#### 7.1.3.3 Toxicology and Safety Pharmacology

Toxicity of E7046 was evaluated in single- and repeated-dose oral toxicity studies in male and female rats and dogs (up to 4 weeks). E7046 induced similar toxicities across preclinical species. Major findings in dogs and rats were limited to dose-dependent intestinal effects and testicular toxicity. Intestinal changes were characterized by abnormal stools which resulted in progressive weight loss at highest dose tested. In addition, E7046 induced minor changes in heart rate and blood pressure (BP) in the dog at exposures more than 2 fold higher than the predicted efficacious human exposure.

The proposed starting dose in humans of 125 mg is less than 1/9 of the human dose equivalent in dogs that caused only occasional mucous stool and slight testicular changes. If translated into the clinic, both would be considered acceptable changes in the intended subject population. Based on the observed toxicities in preclinical species, E7046 may cause the side effects in humans including, but not limited to, the following:

**Gastrointestinal system:** Colitis, characterized by new onset of diarrhea, which may be accompanied by abdominal pain and or gastrointestinal bleeding.

**Testicular system:** Decreased testicular weight, hypo cellularity.

**Cardiovascular system:** Reversible increase in heart rate and decrease in mean blood pressure.

Safety pharmacology of E7046 was evaluated in vitro for hERG channel inhibition and platelet aggregation, in vivo for cardiovascular function in dogs, and for respiratory and central nervous system functions and prostanoid metabolism in rats. No significant adverse effects of E7046 were observed in these studies except for an increase in heart rate, and a decrease of BP at 100 mg/kg of E7046 in dogs. Low risk of side effects in cardiovascular, respiratory and central nervous system is anticipated for E7046 in humans.

Preclinical safety studies thus suggest that E7046 has an acceptable safety profile in the intended population at proposed clinical doses.

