**Table 5 Clinical Laboratory Tests**

Category	Parameters
Hematology	Hematocrit, hemoglobin, platelets, RBC count, and WBC count with differential (bands, basophils, eosinophils, lymphocytes, monocytes, neutrophils) Coagulation panel* : Activated partial thromboplastin time (aPTT), thrombin time, PT, INR, fibrinogen
Chemistry	
Electrolytes	Chloride, potassium, sodium, calcium, phosphorus
Liver function tests	Alanine aminotransferase, alkaline phosphatase, aspartate aminotransferase, total bilirubin
Renal function tests	Blood urea/blood urea nitrogen (UREA/BUN), creatinine
Other	Albumin, cholesterol, HDL, LDL triglycerides, lactate dehydrogenase, , total protein, uric acid. fasting glucose will be done at baseline and after that in conjunction with FDG-PET as per Table 6, or if urine dipstick examination finds glucose or ketones
Urinalysis (dipstick)	Glucose, ketones, protein, and blood. Microscopic examination (if blood or protein is abnormal in dipstick analysis)

RBC = red blood cell, WBC = white blood cell.

\*Coagulation panel: baseline, weekly in cycle 1 and then once every cycle thereafter

Clinical laboratory tests will be performed by site local laboratories. Laboratory certification as available will be included in the final clinical study report for this study.

All hematology, blood chemistry (including pregnancy test, as applicable), and urinalysis samples are to be obtained prior to study drug administration and results reviewed prior to administration/dispensing of study drug at the beginning of each treatment cycle.

A laboratory abnormality may meet the criteria to qualify as an AE as described in this protocol ([Section 9.5.5.1](#)) and the CRF Completion Guidelines. In these instances, the AE corresponding to the laboratory abnormality will be recorded on the Adverse Event CRF.

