#### 9.5.5.8      Pregnancy Test

A serum  $\beta$ -hCG test will be performed for premenopausal women and postmenopausal women who have been amenorrheic for less than 12 months. A 6-mL sample of blood will be taken at designated time points as specified in the Schedule of Procedures/Assessments ([Table 6](#)).

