AE = adverse event,  $\beta$ -hCG = beta-human chorionic gonadotropin, BP = blood pressure, C1D1 = Cycle 1 Day 1, CR = complete response, CRF = case report form, CT = computed tomography, CTCs = circulating tumor cells, DNA = deoxyribonucleic acid, ECG = electrocardiograms, ECOG = Eastern Cooperative Oncology Group,  $^{18}$ FDG-PET =  $^{18}$ fluorodeoxyglucose-positron emission tomography, h = hour, HR = heart rate, irPR = immune-related partial response, irRECIST = immune-related RECIST, IV = intravenous, MDSC = myeloid-derived suppressor cell(s), MRI = magnetic resonance imaging, myeloid-derived suppressor cell, MUGA = multiple gated acquisition, PD = pharmacodynamic, PGE2 = prostaglandin e2, PK = pharmacokinetic, PR = partial response, RECIST = Response Evaluation Criteria In Solid Tumors, RR = respiratory rate, SCCHN = squamous cell carcinoma of head and neck, SAE = serious adverse event, TNBC = triple-negative breast cancer.

- a. The Screening Period extends from Day -28 to Day -1, except for signing of the informed consent form, which may be up to 8 weeks before the first dose of study drug. The baseline assessments may be performed from Day -3 to Day -1 (before the first dose of E7046). Screening assessments may be used as baseline assessments if performed within 72 hours of the first dose of study medication.
- b. The off-treatment assessment should occur within 30 days after the final dose of study treatment. Subjects who discontinue study for reasons other than disease progression will be followed until disease progression or death. All anticancer therapies will be collected (the sponsor may choose to stop the collection of therapies after the first anticancer treatment).
- c. Visit windows are allowed from Cycle 3 onwards as follows: Day 1 ( $\pm$ 3 days), and Day 8 ( $\pm$ 3 days). There must be at least 5 days between the Day 1 and Day 8 visit for any given treatment cycle.
- d. A comprehensive physical examination will be performed at the Screening Visit and at the Off-Treatment Visit. A symptom-directed physical examination will be performed on Day 1 of all treatment cycles and at any time during the study, as clinically indicated.
- e. Vital signs include BP, HR, RR, and body temperature, as well as weight and height. BP, HR, and RR will be collected after the subject has been sitting for 5 minutes. Height will be measured at the Screening Visit only.

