- f. MUGA scans or echocardiograms will be performed at Screening, during the Off-Treatment Visit (window of  $\pm$ 1 week), and if clinically indicated. MUGA scans and echocardiograms will be performed locally in accordance with the institution's standard practice.
- g. A serum pregnancy test ( $\beta$ -hCG) will be performed at screening for all premenopausal women and postmenopausal women who have been amenorrheic for less than 12 months. A urine pregnancy test will be performed at baseline before the first E7046 dose, Cycle 1 Day 1 and at the Off Treatment visit.
- h. 12-Lead ECGs will be collected at the following time points: Screening (single) and Baseline (single unless abnormalities are observed or if clinically indicated, then in triplicate at 2-minute intervals); Day 1 of all cycles (before and after study drug administration); and at the Off-Treatment Visit. In case of any alteration, or if clinically necessary, an echocardiogram and/or cardiac enzymes should be performed.
- i. Continuous Holter/ECGs (12-h/12-lead) to be collected during Cycle 1 on Day 1 and Day 8 at predose (3 timepoints within 45 minutes), and 0.5, 1, 2, 4, 6, 8, and 10 h postdose. At each of these timepoints, subjects should be supinely resting for at least 10 minutes prior to and 5 minutes after the nominal time and the time points when the subject is supinely resting should be recorded. When coinciding, blood draws, vital signs and 12-lead safety ECGs should be performed immediately after the timewindow for ECG extraction.
- j. Hematology and blood chemistry samples will be obtained before drug administration. Screening assessments may be used as baseline assessments if performed within 72 hours of the first dose of study medication. Before drug administration on Cycle 1, Days 1 and 8, a complete blood count should be drawn. Coagulation panel: baseline, weekly in cycle 1 and then once every cycle thereafter. See Table 5 for list of tests.
- k. Urine samples will be obtained before drug administration (either formal urinalysis or urine dipstick for protein and glucose are acceptable).
- l. Genomic DNA samples will be collected at baseline. If it cannot be collected at the designated time point, it may be collected at a time point after baseline.

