- m. All urine excreted will be collected as follows: Cycle 1 Day 1 pre-dose (0-hr) and Cycle 1 Day 1 and Day 8 post-dose to 6hr, 6 to-12hr, 12 to 24hr. Total urine volume collected in each time interval will be recorded. Urine will be analyzed for PK (E7046, M1 metabolite) and PD (PGE-M, metabolite of PGE2).
- n. Blood samples for PK analyses will be collected during Cycle 1 on Day 1 and Day 8 at predose (0 h), 0.5, 1, 2, 4, 6, 8, and 10 and 24h postdose.
- o. Blood samples for PD mRNA and protein biomarker analysis (one PAX gene tube and one lavender top EDTA tube) will be collected at the following time points: predose

(0 h) on Cycle 1 Day 1, 24 h after first dose, Day 8, and Day 15. Blood for cell free nucleic acid will be collected at C1D1 predose, at each tumor assessment, and at the end of treatment. Blood for MDSC in circulation will be collected at baseline, C1D1 predose, C1D8, C1D15, C2D1, C3D1, and C5D1.

- p. Paired tumor biopsies will be obtained, with appropriate subject consent. Subjects will have the biopsy before the first dose of E7046 and during Cycle 2, as long as the subject has had uninterrupted treatment at least 5 days prior to biopsy. In addition, archived fixed tumor tissue will be collected if available (instructions to be provided in a separate manual).
- q. FDG PET/CT scans should be performed according to instructions provided by the imaging core lab and sent to the core lab for quantitative assessments. Scans should be performed at baseline (within 7 days before C1D1) for all subjects, repeat scans in conjunction with the Week 6 and Week 12 tumor assessments timepoints only for subjects with evidence of evaluable FDG avid tumor lesion(s) at screening. FDG-PET/CT scan timepoints may be changed based on emergent data. Subjects must have a fasting serum glucose assessment performed before injection of the PET tracer for each scan. FDG-PET/CT will not be performed if serum glucose is >120 mg/dl for nondiabetics or >200 mg/dl for diabetic subjects.

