- r. Tumor assessments will be performed based on irRECIST and modified RECIST1.1. Treatment decisions will be based on irRECIST. Tumor assessments will be carried out during the Pretreatment Phase and then every 6 weeks (during the 6th week; counting from C1D1) during treatment cycles in both the Treatment Phase and the Extension Phase. CT scans (with oral and intravenous contrast) of chest, abdomen, and pelvis and of other known sites of disease will be obtained at Screening (within 28 days prior to Cycle 1/ Day 1), using the above tumor assessment schedule, and as indicated clinically. Skin lesions may only be considered as non-index lesions (no photographs required) or as new lesions to add to the tumor burden sum. Subjects with SCCHN must also have head and neck scans performed at all tumor assessment timepoints.
- MRI scans may be used instead of CT scans for (head, neck) abdomen and pelvis; however, chest must be assessed using CT. Chest disease may not be followed using chest x-ray. CT scans should be performed with oral and iodinated IV contrast and MRI scans with IV gadolinium chelate unless there is a medical contraindication to contrast. If iodinated IV contrast is contraindicated, chest CT should be performed without IV contrast. The same method of assessment must be used at all time points as used at Screening.
- s. Screening brain scans will be performed by MRI pre- and post- gadolinium or CT with contrast within 4 weeks prior to C1D1. During the Treatment Phase, CT/MRI of the brain will be performed if clinically indicated, and within a target of 1 week after a subject achieves a irCR. For subjects with history of treated brain metastases, brain scans will be performed at every tumor assessment time point. The same methodology and scan acquisition techniques used at screening should be used throughout the study to ensure comparability.

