### 9.5.8.2 Reporting of Pregnancy and Exposure to Study Drug Through Breastfeeding

Any pregnancy in which the estimated date of conception is either before the last visit or within 28 days of last study treatment or any exposure to study drug through breastfeeding during study treatment or within 28 days of last study treatment must be reported.

If an adverse outcome of a pregnancy is suspected to be related to study drug exposure, this should be reported regardless of the length of time that has passed since the exposure to study treatment.

A congenital anomaly, death during perinatal period, an induced abortion, or a spontaneous abortion are considered to be an SAE and should be reported in the same time frame and in the same format as all other SAEs ([Section 9.5.8.1](#)).

Pregnancies or exposure to study drug through breastfeeding must be reported by fax or email as soon as possible but no later than 1 business day from the date the investigator becomes aware of the pregnancy. The contact information for the reporting of pregnancies and exposure to study drug through breastfeeding is provided in the Investigator Study File. The Pregnancy Report Form must be used for reporting. All pregnancies must be followed to outcome. The outcome of the pregnancy must be reported as soon as possible but no later than 1 business day from the date the investigator becomes aware of the outcome.

A subject who becomes pregnant must be withdrawn from the study. A subject who becomes pregnant may remain in the study if the investigator judges that the potential benefit to the subject outweighs any potential risk to the subject or the fetus and the subject gives informed consent for the further participation.

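### Protocol Table 6 schedules no pregnancy test between Cycle 1 Day 1 and the Off-Treatment Visit, which is 126 daily doses and three tumor assessments in a 6-cycle course

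*Protocol*

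**What the plan says.** Protocol Table 6 marks the pregnancy test at Screening, Baseline, Cycle 1 Day 1 and one late visit. The cell for Day 1 of Cycle 2 and beyond is empty, whereas the ECOG and 12-lead ECG rows have an entry there. Footnote g specifies serum at Screening and then: "A urine pregnancy test will be performed at baseline before the first E7046 dose, Cycle 1 Day 1 and at the Off Treatment visit". That identifies the late visit as Off-Treatment, for which footnote b says: "The off-treatment assessment should occur within 30 days after the final dose of study treatment".

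Three other protocol sections bear on the point:

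- **Section 9.5.5.8** describes only a serum test ("A 6-mL sample of blood will be taken at designated time points") and refers to Table 6 for the visits.
- **Section 9.5.5.3**, below Table 5, names "blood chemistry (including pregnancy test, as applicable") among the samples to be taken before dosing, with results reviewed before drug is dispensed at the start of each cycle. It lists no visits for the test.
- **Section 9.5.8.2** says: "A subject who becomes pregnant must be withdrawn from the study". The next sentence lets her stay if the investigator judges the benefit to outweigh the risk and she consents.

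The SAP's copy of the schedule (Section 13.1, Table 3, footnote g) differs. It has a urine test on Day 1 of every cycle and none at Off-Treatment.

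**The concern.** This is a first-in-human study with open-ended daily dosing. The protocol's toxicology summary (Section 7.1.3.3) says: "Toxicity of E7046 was evaluated in single- and repeated-dose oral toxicity studies in male and female rats and dogs (up to 4 weeks"). It mentions no embryo-fetal study, so the protocol itself gives no basis for judging fetal risk over longer exposure. Eligible tumors include cervical and triple-negative breast cancer, and the lower age limit is 18, so women of childbearing potential can be expected among the participants.

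Section 9.5.8.2 calls for a decision once a pregnancy is known: withdrawal, or a risk-benefit judgment with consent. No scheduled on-treatment test would bring a pregnancy to light. Drug exposure could continue until symptoms appear or the woman reports it.

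Imaging falls in the same interval. Footnote r of Table 6 says: "Tumor assessments will be carried out during the Pretreatment Phase and then every 6 weeks", covering chest, abdomen and pelvis. Footnote q adds FDG-PET/CT for PET-evaluable subjects: "repeat scans in conjunction with the Week 6 and Week 12 tumor assessments timepoints".

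**Working it through.** The documents state no figure on this point, so there is none to reproduce. The check is schedule arithmetic.

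**Inputs (protocol)**

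- Dosing once daily, continuous, in 21-day cycles (Section 9.4.1).
- Last test before the gap: Cycle 1 Day 1, taken as Day 1. Next test: Off-Treatment Visit, up to 30 days after the last dose (Table 6, footnotes g and b).
- Tumor assessments during every sixth week from Cycle 1 Day 1 (footnote r).
- Day 1 visit window of ±3 days from Cycle 3 (footnote c).
- Six cycles as the main example, because Section 9.7.1 sets the data cutoff by the last enrolled subject completing 6 cycles.
- Assumed: no dose interruption and assessments done on time.

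**Current schedule**

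For n cycles, doses = 21n, and the longest time from Cycle 1 Day 1 to the next test = 21n + 30 − 1 days.

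| Cycles | Doses with no further scheduled test | Longest time to next test |
|---|---|---|
| 2 | 42 | 71 days |
| 4 | 84 | 113 days |
| 6 | 126 | 155 days |

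The last 30 days of each interval are off drug.

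The Week 6, 12 and 18 assessments fall on Days 36–42, 78–84 and 120–126. Subtracting Day 1, they come 35–41, 77–83 and 119–125 days after the last test.

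**With a test on Day 1 of every cycle**

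- Added tests over 6 cycles: Days 22, 43, 64, 85 and 106, so five.
- Longest run of dosing between tests: 21 days, or 21 + 3 + 3 = 27 with the windows.
- Test preceding each assessment: Day 22 for Week 6 (36 − 22 = 14 to 42 − 22 = 20), Day 64 for Week 12 (78 − 64 = 14 to 84 − 64 = 20) and Day 106 for Week 18 (120 − 106 = 14 to 126 − 106 = 20). Each follows a test by 14–20 days.
- Longest time to the Off-Treatment test: Day 106 to Day 156, which is 50 days (21 of them dosing days) against 155 now.

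**Does Section 9.5.5.3 supply the missing test?** It governs when samples are taken and reviewed, qualifies the pregnancy test with *as applicable*, and refers to Table 6 for the visits. Table 6 has none after Cycle 1 Day 1 until Off-Treatment. It also places the test under blood chemistry, while footnote g uses urine after Screening. It therefore does not schedule a test, though a site could be unsure whether one is expected.

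**The case against.** The strongest argument is that Section 9.5.5.3 can be read as expecting a pregnancy result before each cycle, since it groups the test with chemistry samples that Table 6 does schedule on Day 1 of later cycles. On that reading the fault is an ambiguity. This stands in part: the text is ambiguous. But a site that follows Table 6 and footnote g exactly performs no on-treatment test after Cycle 1 Day 1.

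The SAP schedule may come from an earlier protocol version: SAP Section 7 cites v1.0, while SAP Section 3 cites Amendment 01. If so, per-cycle testing may have been removed on purpose. That is an inference, and the protocol gives no reason for such a removal. Sites follow the protocol, so the mismatch itself does not change conduct.

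Existing controls are real. There are three tests before or at the first dose, highly effective contraception plus a condom until 30 days after the last dose, adverse-event review at every visit and a symptom-directed examination each cycle. They make an undetected pregnancy less likely, but none of them is an on-treatment test.

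Several limits also stand:

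- Six cycles is illustrative; the documents give no expected treatment duration.
- Of the 126 doses, the 21 in Cycle 1 follow the existing test either way. The change puts a new test before the other 126 − 21 = 105.
- A test 14–20 days before a scan can miss a very recent conception.
- MRI may replace CT for abdomen and pelvis.
- The toxicology section is a summary, and the Investigator's Brochure is not available here. An embryo-fetal study may exist outside these documents.

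**Conclusion.** The concern holds. The protocol's schedule leaves women of childbearing potential without a pregnancy test from Cycle 1 Day 1 to the Off-Treatment Visit. Over 6 uninterrupted cycles that covers 126 doses and three tumor assessments, with up to 155 days to the next test; over 2 cycles it is 42 doses and up to 71 days. Only women of childbearing potential are affected, and the documents do not give their number. The point concerns participant safety and does not touch the DLT rules, the MTD or RP2D decision, or any analysis. It should be corrected because the exposure is avoidable at little cost.

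**What to change.** 1. In protocol Table 6 and footnote g, add a urine pregnancy test on Day 1 of every cycle, before study drug is dispensed, for women of childbearing potential as defined in Inclusion Criterion 19. Keep the Screening serum test and the Off-Treatment urine test.
2. Require serum confirmation of a positive urine test, and hold study drug until that result is known.
3. In Section 9.5.5.3, replace the *as applicable* qualifier with an explicit reference to women of childbearing potential.
4. In Section 9.5.5.8, state serum at Screening and urine thereafter.
5. Align SAP Section 13.1, Table 3 and its footnote g, including the Off-Treatment test it lacks.

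**Cost.** Five extra urine tests per affected woman over 6 cycles. The upper bound is 5 × 40 = 200 tests, if all 40 subjects were such women and all completed 6 cycles. Table 6 already schedules urinalysis on Day 1 of Cycle 2 and beyond, so no visit or sample is added. A false-positive urine result can delay a dose until serum confirmation. The change needs a written amendment under Section 11.1, with regulatory submission and IRB/IEC approval if it is classed as specifically affecting subject safety.

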### 9.5.6.2 Description of Procedures/Assessments Schedule

Please refer to the footnotes in the table of the Schedule of Assessments.

### 9.5.7 Appropriateness of Measurements

All clinical assessments are standard measurements commonly used in oncology studies.

The safety assessments to be performed in this study, including hematology analyses, blood chemistry tests, urinalysis, radiologic studies, and assessment of AEs, are standard evaluations to ensure subject safety.

### 9.5.8 Reporting of Serious Adverse Events, Pregnancy, and Events Associated with Special Situations

#### 9.5.8.1 Reporting of Serious Adverse Events

**All SERIOUS ADVERSE EVENTS, regardless of their relationship to study treatment, must be reported on a completed SAE form by email or fax as soon as possible but no later than 24 hours from when the investigator becomes aware of the event.**

Serious adverse events, regardless of causality assessment, must be collected through the last visit and for 30 days after the subject's last dose. All SAEs must be followed to resolution or, if resolution is unlikely, to stabilization. Any SAE judged by the investigator to be related to the study treatment or any protocol-required procedure should be reported to the sponsor regardless of the length of time that has passed since study completion.

